Organ System	Signs/Symptoms
Cardiovascular	Tachycardia, hypotension
Coagulation	Disseminated intravascular coagulation (DIC) characterized by elevated D-dimer, hypofibrinogenemia, bleeding
Renal	Azotemia
Hepatic	Transaminitis, hyperbilirubinemia
Neurologic	Altered mental status, confusion, delirium, aphasia, hallucinations, tremor, seizures, ataxia

CRS Grading/Severity

The outlined clinical grading criteria, based on NCI CTCAE v4.0, is designed to guide clinicians in the management of CRS. Many of the signs and symptoms associated with CRS can also be attributable to other common complications of cancer therapy such as neutropenic fever, other infectious complications, and tumor lysis syndrome. Thus, in applying the criteria below, clinicians should exercise appropriate clinical judgement in each patient-specific scenario in an effort to distinguish true CRS from other cancer treatment-related toxicities. This will ensure appropriate delivery of care and avoidance of therapies that may otherwise not be indicated.

Page	143	of 154	

Grade 1 – Mild (Symptomatic Management)
Symptoms largely limited to constitutional symptoms listed above (Table 14)
Only requires symptomatic management
Grade 2 – Moderate (Moderate Intervention)
Hypotension responsive to fluids or single, low dose vasopressor
Oxygen requirement <40%
Grade 2 organ toxicity
Grade 3 – Severe (Aggressive Intervention)
Hypotension requiring high dose or >1 vasopressor
Oxygen requirement ≥40%
Grade 3 organ toxicity
Grade 4 transaminitis
Grade 4 – Life-threatening (Life-sustaining intervention)
Ventilator support required
Grade 4 organ toxicity, excluding transaminitis
Grade 5 – Death
Death

Table 15CRS Grading

MANAGEMENT OF CRS

MANAGEMENT OF CRS

Management of CRS involves both supportive measures and pharmacologic therapies that inhibit immune activation and amplification. Supportive measures are directed at managing constitutional symptoms and achieving and maintaining hemodynamic stability. Immune targeted therapies are directed at the cytokines released in the pathobiology of the syndrome. Cytokines identified to play a role in CRS include, but are likely not limited to, TNF α , IFNy, IL-1 β , IL-2, IL-5, IL-6, IL-8, and IL-10. Therapies utilized in CRS exhibit either a non-specific inhibition of immune amplification or a more targeted inhibition of a particular cytokine. These therapies are outlined below.

Tocilizumab

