 CV: Hypotension (SBP <90 mmHg e ≥ 20% decrease in baseline SBP or DBP) unresponsive to fluids and low dose vasopressors given for grade 2 CRS (Table 17) +/- symptomatic tachycardia Pulmonary: Decreased O2 saturatio (≤88%) requiring >40% to achieve saturation ≥93% Neuro: Neurologic symptoms (confusion, AMS, seizure) Renal: Scr > 3.0 – 6.0 x ULN and/or 	 measures outlined under Grade 1 and 2 CRS Increase supplemental O2 to achieve saturation ≥93% High dose or multiple vasopressors (Table 17) Tocilizumab as outlined in Grade 2 CRS Dexamethasone 10 mg IV q6h if
 Scr > 3.0 x above baseline or > 4.0 	refractory to tocilizumab

LCCC1524-ATL Administration of T lymphocytes Expressing the CD30 Chimeric Antigen Receptor (CAR) for Prevention of Relapse of CD30+ Lymphomas after High Dose Therapy and Autologous Stem Transplantation (ATLAS) ATLCAR.CD30

Page	147	of 154	

 Hepatic: AST/ALT > 5.0 - 20.0 x ULN and/or T. Bili > 3.0 -10.0 x ULN Grade 4 CRS 	
 CV: Persistent hemodynamic instability (hypotension and tachycardia refractory to aggressive fluids and pressor support) Pulmonary: Hypoxic respiratory failure: O2 saturation ≥93% not able to be achieved with supplemental O2 (nasal cannula, non-rebreather) Neuro: Neurologic symptoms (confusion, AMS, seizures) Renal: Scr > 6.0 x ULN Hepatic: AST/ALT > 20.0 x ULN and/or T. Bili > 10.0 x ULN 	 Continue monitoring and supportive measures outlined in Grade 1, 2, and 3 CRS Continue/initiate vasopressors, tocilizumab, and dexamethasone as outlined in Grade 3 CRS Ventilatory support Dialysis if indicated (CVVHD or HD)

Table 17.High dose vasopressors in adult patients

Vasopressor	Dose (high dose)*
Norepinephrine	\geq 20 mcg/min monotherapy
Dopamine	$\geq 10 \text{ mcg/kg/min}$
Phenylephrine monotherapy	\geq 200 mcg/min
Epinephrine	$\geq 10 \text{ mcg/min}$
Vasopressin + additional vasopressor	Vasopressin + norepinephrine equivalent of $\geq 10 \text{ mcg/min}$

Confidential

*Vasopressors at doses lower than those outlined are considered low dose vasopressors

Table 18.Pediatric CRS Treatment Algorithm

Signs/Symptoms	Management		
Grade 1 CRS			

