 Fever (≥ 38.00 C) +/- additional constitutional symptoms (rigors, malaise, fatigue, anorexia, myalgias/arthralgias, nausea/vomiting) Renal: Scr >ULN – 1.5 x ULN and/or Scr 1.5 – 2.0 x above baseline and/or Scr increase > 0.3 mg/dL from baseline Hepatic: AST/ALT > ULN – 2.5 x ULN and/or T.bili > ULN – 1.5 x ULN 	 Complete infectious workup (Cultures, Chest XR/CT, etc.) Daily weights; accurate I/Os Vital signs q30 mins. until symptom resolution Initiate empiric antibiotics Supportive measures: acetaminophen prn fevers; ondansetron or prochlorperazine prn nausea/vomiting; meperidine/morphine prn rigors 		
Grade	2 CRS		
 CV: Hypotension +/- asymptomatic tachycardia (Table 19 & Table 20) Pulmonary: Decreased O2 saturation (≤88%) 	 Continue monitoring and supportive measures outlined under Grade 1 CRS Supplemental O2 up to 40% to saturation ≥93% 		
 Renal: Scr ≥ 1.5 - 3.0 x ULN and/or Scr 2.0 - 3.0 x above baseline Hepatic: AST/ALT > 2.5 - 5.0 x ULN and/or T. Bili > 1.5 - 3.0 x ULN 	 Fluid bolus: 20 mL/kg (Max: 1000 mL) IV over 1-2 hours; Low dose vasopressor (Table 21) if unresponsive to fluid bolus Tocilizumab 		

anspl R.CI	lantation (ATLAS) D30	Page 149 of 15-
		 - <30 kg: 12 mg/kg IV over 1 hour x 1 dose; May repeat every 8 hours for a max of 3 additional doses if no improvement from initial dose - ≥30 kg: 8 mg/kg IV over 1 hour x 1 dose (Max individual dose: 800 mg); may repeat every 8 hours for a max of 3 additional doses if no improvement from initial dose
	Grade	3 CRS
•	CV: Hypotension unresponsive to fluids and low dose vasopressors given for grade 2 CRS +/- symptomatic tachycardia (Table 19 & Table 20))	• Continue monitoring and supportive measures outlined under Grade 1 and 2 CRS
•	Pulmonary: Decreased O2 saturation (≤88%) requiring >40% to achieve saturation ≥93%	 Increase supplemental O2 to achieve saturation ≥93% High dose or multiple vasopressors
•	Neuro: Neurologic symptoms (confusion, AMS, seizure)	 (Table 21) Tocilizumab as outlined in Grade 2 CRS
•	Renal: $Scr > 3.0 - 6.0 \times ULN$ and/or \circ Scr > 3.0 x above baseline or > 4.0	• Dexamethasone 0.1 mg/kg (Max 10 mg) IV q6h if neurologic symptoms
•	Hepatic: AST/ALT > 5.0 – 20.0 x ULN and/or	present or refractory to tocilizumab
	• T. Bili > $3.0 - 10.0 \text{ x ULN}$	
	Grade	4 CRS
•	CV: Persistent hemodynamic instability (hypotension and tachycardia refractory to aggressive fluids and pressor support)	• Continue monitoring and supportive measures outlined in Grade 1, 2, and 3 CRS

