LCCC1524-ATL Administration of T lymphocytes Expressing the CD30 Chimeric Antigen Receptor (CAR) for Prevention of Relapse of CD30+ Lymphomas after High Dose Therapy and Autologous Stem Transplantation (ATLAS) ATLCAR.CD30

•	Pulmonary: Hypoxic respiratory failure: O2 saturation ≥93% not able to be achieved with supplemental O2 (nasal cannula, non-rebreather)	•	Continue/initiate vasopressors, tocilizumab, and dexamethasone as outlined in Grade 3 CRS Ventilatory support
•	Neuro: Neurologic symptoms (confusion, AMS, seizures)	•	Dialysis if indicated (CVVHD or HD)
•	Renal: Scr $> 6.0 \times ULN$		11 D)
•	Hepatic: AST/ALT > 20.0 x ULN and/or		
	\circ T. Bili > 10.0 x ULN		

Table 19.Definition of hypotension in pediatric patients

Age	Hypotension (SBP)
0 – 28 days	< 60 mmHg
1-12 months	< 70 mmHg
1-10 years	< 70 mmHg + (age x 2)
>10 years	< 90 mmHg

Table 20.Definition of tachycardia in pediatric patients

Age	Tachycardia (HR at Rest)	Tachycardia (HR while Awake)
0-3 months	> 160 BPM	> 205 BPM
3 months - 2 years	> 160 BPM	> 190 BPM
2-10 years	> 90 BPM	> 140 BPM
>10 years	> 90 BPM	> 100 BPM

Vasopressor	Dose (high dose)*
Norepinephrine	$\geq 2 \text{ mcg/kg/min}$
Dopamine	$\geq 10 \text{ mcg/kg/min}$
Phenylephrine monotherapy	\geq 5 mcg/kg/min
Epinephrine	$\geq 1 \text{ mcg/kg/min}$
Vasopressin	> 100 milliunits/kg/hr

Table 21.High dose vasopressors in pediatric patients

*vasopressors at doses lower than those outlined are considered low dose vasopressors

References

- 4. National Cancer Institute Common Terminology Criteria for Adverse Events v4.03; 2010. Available online at: http://evs.nci.nih.gov/ftp1/CTCAE/About.html (accessed 11/28/2015).

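### Table 21 sets the pediatric high-dose cut-off for norepinephrine and epinephrine above the adult one at any weight over 10 kg, so identical pressor support can be grade 3 CRS at age 18 and grade 2 at 17

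*Combined protocol and SAP*

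**What the plan says.** Appendix VIII (Section 18.8) has one CRS grading table and separate vasopressor tables for adults and children.

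- **Table 15, grade 2:** "Hypotension responsive to fluids or single, low dose vasopressor".
- **Table 15, grade 3:** "Hypotension requiring high dose or >1 vasopressor".
- **Table 17 (adults):** high-dose norepinephrine starts at "20 mcg/min monotherapy", epinephrine at 10 mcg/min and phenylephrine at 200 mcg/min.
- **Table 21 (children):** the same three drugs are high dose from 2, 1 and 5 mcg/kg/min, with no absolute maximum. Its footnote adds that "vasopressors at doses lower than those outlined are considered low dose vasopressors"; Table 17 carries the same footnote.
- **Table 18 (pediatric algorithm):** the grade 2 row gives fluid at "20 mL/kg (Max: 1000 mL) IV over 1-2 hours; Low dose vasopressor (Table 21) if unresponsive to fluid bolus". The grade 3 row is "Hypotension unresponsive to fluids and low dose vasopressors given for grade 2 CRS".

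Sections 5.1 and 5.2 class ages 3 to 17 as pediatric and 18 or over as adult. Section 4.1.3 makes grade 3 or 4 CRS a DLT if it lasts more than 72 hours. Section 11.2 includes adults and children in one MTD estimate.

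**The concern.** The CRS grade is an input to the primary endpoint. For a subject on one vasopressor with no other grade 3 feature, the boundary between grades 2 and 3 is the high-dose cut-off. That cut-off jumps at the 18th birthday, in the direction that requires a larger absolute rate in the child.

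Table 15 does not cite Table 21, but Table 18 does, so Table 21 is the natural definition of low dose for a child. Nothing in the protocol reconciles the two tables or says which governs DLT grading. Two subjects of the same weight on the same infusion, a few months apart in age, could enter the CRM as one DLT and one non-DLT.

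**Working it through.** **Cut-offs.** The break-even weight is the adult flat rate divided by the pediatric per-kg rate. The documents give no subject weights; 15 and 60 kg are assumed.

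| Drug | Table 17 (mcg/min) | Table 21 (mcg/kg/min) | Break-even | Pediatric cut-off at 15 kg | at 60 kg |
|---|---|---|---|---|---|
| Norepinephrine | 20 | 2 | 20/2 = 10 kg | 30 (1.5 times adult) | 120 (6 times) |
| Epinephrine | 10 | 1 | 10/1 = 10 kg | 15 (1.5 times) | 60 (6 times) |
| Phenylephrine | 200 | 5 | 200/5 = 40 kg | 75 (0.375 times) | 300 (1.5 times) |

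Dopamine is 10 mcg/kg/min in both tables. Vasopressin alone has a rate only in Table 21.

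**Grade.** Take a 60 kg subject on norepinephrine alone at 50 mcg/min. At 18, 50 is above 20: high dose, grade 3. At 17, 50 is below 2 × 60 = 120: low dose, grade 2. The discordant range at 60 kg is 20 to just under 120 mcg/min for norepinephrine and 10 to just under 60 for epinephrine.

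**DLT.** Beyond 72 hours, and if judged at least possibly related, the 18-year-old meets the CRS DLT criterion. The 17-year-old does not on grade alone. The footnote to the DLT definition opens with grade 3 and 4 reactions, which would leave this subject out. It then names hypotension needing pressors without giving a dose, which could be read to count this subject.

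**CRM effect of one such event.** I used Section 11.1: DLT probability a^b, a = (0.0281, 0.0568, 0.1), b exponential with mean 1, target 10%, complete follow-up. The section does not say whether the posterior mean of b is plugged in or the DLT probabilities themselves are averaged, so both were run. Suppose subject 7, at level 3, is the discordant case after 0/2, 0/2, 0/2.

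*Plug-in posterior mean of b:*
- Not counted (0/2, 0/2, 0/3): level 3 estimate 1.6%; stay at level 3.
- Counted (0/2, 0/2, 1/3): estimates 5.1%, 9.1%, 14.6%; subjects 8 and 9 go to level 2.
- No further DLT: the MTD is level 3 either way, with level 3 estimates of 0.9% vs 9.1% at N = 12 and 0.6% vs 5.9% at N = 18.
- One further DLT, N = 12: in subject 10, 11 or 12, the MTD is level 3 if the event is not counted and level 2 if it is; in subject 8 or 9, level 3 against level 1.
- One further DLT, N = 18: in subjects 8 to 13, level 3 against level 2; in subjects 14 to 18, level 3 both ways.

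*Posterior-mean DLT probabilities, event alone:*
- N = 12: level 3 (3.8%) if not counted, level 2 (9.1%) if counted.
- N = 18: level 3 both ways (2.5% vs 9.6%).

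**Effect of a lower-of rule.** For norepinephrine, min(2 × kg, 20) is 20 mcg/min at every weight from 10 kg, so the step at 18 disappears. Per kg this is 1.33 at 15 kg and 0.33 at 60 kg, so a smaller child is not held to a lower per-kg limit than a 60 kg adult (20/60 = 0.33). For phenylephrine, min(5 × kg, 200) is 75 at 15 kg and 200 from 40 kg.

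**The case against.** The strongest reply is that no error has been shown. The appendix is a management guideline with deliberately separate adult and pediatric criteria; Tables 19 and 20 are age-specific by design. It tells clinicians to "exercise appropriate clinical judgement in each patient-specific scenario". Section 4.1.3 adds FDA consultation on relatedness, and Section 10.4 has each DLT discussed as it occurs. On the dose-free reading of the DLT footnote, both subjects count and the discordance vanishes. The case also needs a child, one vasopressor, a rate between the cut-offs, more than 72 hours, possible relatedness and no other grade 3 criterion. Section 1.5.5 reports no CRS in nine earlier subjects at these dose levels.

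Much of this stands. A reader might infer that the Table 21 rates are a mistake because the same algorithm caps other weight-based amounts at the adult figure (fluid at 1000 mL; "Dexamethasone 0.1 mg/kg (Max 10 mg) IV q6h"). That is suggestive only: those are amounts given to a patient, whereas Table 21 is a classification threshold for a titrated infusion. The documents do not settle intent.

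What does not stand is that judgment resolves the matter. None of the safeguards says which cut-off governs, and an ambiguous footnote is better settled before an event than after one.

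**Conclusion.** The mismatch is real and follows exactly from the two tables: above 10 kg for norepinephrine and epinephrine, above 40 kg for phenylephrine. The split between grades 2 and 3 follows through Table 15. The DLT split is possible, not certain, because it depends on how the footnote is read.

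Three stronger readings are not supported:
- **That the plan hides pediatric toxicity or biases the MTD.** No direction of bias is claimed, and the case is rare. The documents give neither the number of children nor their CRS rate, so its frequency cannot be estimated.
- **That one such event changes the MTD.** It can change the next assignments. With the plug-in estimate and no further DLT the MTD is the same; with averaged probabilities it differs at N = 12 but not at N = 18.
- **That it can change the MTD only if another DLT follows.** That holds for the plug-in estimate alone.

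The CRM figures rest on the assumed sequence and on placing the event at subject 7. Severity is minor; the reason to act is that the ambiguity is cheap to remove.

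**What to change.** 1. Confirm the Table 21 norepinephrine and epinephrine entries with the clinical authors, and correct them if wrong. This comes first, because a correction may make the next step unnecessary.
2. With clinical sign-off, add to the Table 21 footnote: for a subject under 18, a single vasopressor is high dose at the lower of the Table 21 rate times body weight and the Table 17 absolute rate. Dopamine and vasopressin alone are unchanged.
3. State in Section 4.1.3 that the DLT rule, including its footnote on pressor-requiring hypotension, uses this cut-off. Applying it requires drug, rate, duration and body weight to be on record for each CRS event.

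**Cost.** No extra patients or procedures, but an amendment with IRB approval before implementation (Section 14.0), and a decision on any pediatric CRS already graded. Above 10 kg the adult flat rate in effect replaces Table 21's norepinephrine and epinephrine rates, so this is more than a cap at the margin. Some pediatric CRS moves from grade 2 to grade 3, where Table 18 adds more oxygen, high-dose or multiple vasopressors, and dexamethasone for neurologic symptoms or tocilizumab-refractory CRS. Expedited CRS reporting is unaffected, since Section 10.3.3 starts it at grade 4. Below 40 kg the pediatric phenylephrine cut-off stays lower than the adult one.

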18.9 APPENDIX IX - Neurotoxicity Treatment Algorithm

Version 1.0, November 2, 2017

BACKGROUND

Neurotoxicity from CAR-T therapy can occur as part of cytokine release syndrome (CRS) or as an independent process. The underlying pathophysiology for neurologic toxicity from CAR-T therapy is not fully understood. CAR-T cells in the CNS may play a role. However, the heightened systemic inflammatory and cytokine state resulting from CAR-T therapy may also be a factor, as other therapies associated with increased cytokine levels have also been associated with neurologic toxicities, such as high-dose interleukin-2 (IL-2) and blinatumomab.

The symptoms and manifestations of neurotoxicity are broad and range from confusion/altered mental status to seizures. Routine monitoring is critical in patients receiving CAR-T therapy to identify neurologic symptoms early and neurology should be consulted for any patients that exhibit early signs/symptoms of neurotoxicity. Early interventions should be employed to prevent worsening, especially if therapies are already indicated such as corticosteroids.

Neurotoxicity grading should follow CTCAE v4.03.

Note that tocilizumab has no clear role in managing CAR-T-induced neurotoxicity, largely because tocilizumab is not thought to penetrate the central nervous system (CNS). If neurotoxicity occurs with concomitant CRS then tocilizumab should be employed per CRS management algorithm to treat CRS, but for neurotoxicity in the absence of CRS, tocilizumab should generally not be used.

Table 22.	Neurotoxicity Treatment Algorithm	
-----------	-----------------------------------	--

Signs/Symptoms	Management
Grade 1-2 neurotoxicity, excluding seizures	
• Non-life threatening symptoms which may include: moderate headaches not responding to oral medications, confusion, dizziness, hallucinations,	• Notify covering providers, including oncology (CAR-T) attending physician.
tremor, or psychiatric changes.	• Ensure other etiologies have been excluded as much as possible, such as

IK.CD30	1 age 155 01 154
 Grade 1: Symptoms are mild and do not substantially impair function. Grade 2: Symptoms are moderate and may impair function such as conducting instrumental activities of daily living (IADL's) like self-administering medications or using a telephone, but NOT activities of daily living (ADL's) such as dressing, walking or bathing. Any generalized seizures should be managed as grade 3 or greater events (see below). 	 infection or toxicity from other medications. If not already admitted, admit to inpatient for grade 2 or rapidly worsening grade 1. Daily neurological exam including mini-mental status exam. Consider urgent MRI brain with and without contrast. Consider lumbar puncture to evaluate for infection. If sufficient material is available these samples may also be used for CAR T cell and cytokine analysis.
 Grade 3 neurotoxicity or any non-sustained Symptoms may be severe and impair 	Notify covering providers, including
 ADL's (listed above). Symptoms may include confusion/altered mental status, disorientation, aphasia, tremor, stupor, loss of consciousness, hallucinations, unstable balance, cranial nerve deficits, or psychiatric changes. Any non-sustained / non-recurrent generalized seizures should be managed as a grade 3 neurological event. 	 oncology fellow and oncology (CAR-T) attending If not already admitted, admit to inpatient floor bed with seizure precautions. Consider stepdown / ICU, particularly if event is a seizure. Neurological exam at least every 8 hours plus daily mini-mental status exam. Consult neurology service.
• Likely or definite strokes should be managed as a grade 4 neurological event.	 Obtain urgent MRI brain with and without contrast if feasible. Obtain lumbar puncture to evaluate for infection if feasible. If sufficient material is available these samples may also be used for CAR T cell and cytokine analysis.

	 Give corticosteroids as indicated below for any grade 3 neurotoxicity or for generalized seizures of any duration. Dexamethasone: Adults: 10 mg IV q6h Pediatrics: 0.1 mg/kg (Max 10 mg) IV q6h Continue corticosteroids until symptoms have improved to Grade 1 or resolved completely. If seizure activity, add levetiracetam 500 mg PO BID and/or other antiepileptics as
appropriate. Grade 4 neurotoxicity, any recurrent / sustained generalized seizures, or any stroke	
 Life threatening symptoms including recurrent or sustained generalized seizures, or obtundation. 	 Notify covering providers, including oncology fellow and oncology (CAR- T) attending.
• Likely strokes should be managed as grade 4 neurological events until if and when stroke is excluded as a	• Manage as grade 3 event as above, but admit to ICU.
probable diagnosis.	• If stroke is felt to be possible, call CODE STROKE and notify Brain Attack Team (BAT).

References:

